### **Concomitant Medications/Treatments**

As part of the initial psychiatric evaluation, a detailed history of past and present treatments (pharmacological and non-pharmacological) will be obtained. At each study visit, subjects will be assessed for the use of concomitant medication. The guidelines for use of concomitant medications/treatments during the study are as follows:

- Participants may continue treatment with concomitant psychotropic medications (provided no exclusion criteria are met) and must remain on a stable dose during the course of the trial.

## Photobiomodulation in ASD

- Subjects requiring initiation of acute or chronic medication treatment may be discontinued from the study if treatment is judged by the investigator to interfere with the assessment of study drug effect.
- Non-pharmacological treatments such as supportive individual, family, or group therapy will be permitted provided they were in place for a substantial period of time (>1 month) prior to study enrollment and remain unchanged during the course of the trial.
- No new non-pharmacological treatments may be initiated during the course of the trial.

### **Washout Period**

After the screening period, subjects who are currently taking prohibited medications as noted in exclusion criteria, and willing to discontinue the use of their medication may do so in order to be eligible for participation in this study, if clinically appropriate per clinician judgment. If

## Photobiomodulation in ASD

appropriate, medication washout will be recommended by our clinicians to participants and current providers. Clinicians will determine a washout schedule based on the half-life of the medication, the adverse effects associated with treatment and withdrawal, and an assessment of individual factors including duration on drug and dose. No subjects will be asked to discontinue ongoing exclusionary medications to participate in the study; however, if the subject is already tapering the medication off for clinical reasons at the time of screening and evaluation for participation, they will be considered eligible to participate only after the washout period as described. Our office does not take over care for the patient, but remains available during this time period. The washout schedule will be discussed with the participant and current providers.

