### **3. LENGTH OF STUDY**

This study will last up to 12 weeks from enrollment (allowing up to four weeks from the date of consent to schedule and complete the initial screening process). Once subjects have completed the screening process and baseline characterization, they will begin the 8-week open-label trial. Subjects will be assessed on measures of efficacy and safety every week throughout the study.

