The subject will meet all the inclusion criteria, have none of the exclusion criteria, and will provide their electronic signature on the Informed Consent and Assent documents (when applicable) to participate in this clinical study. Any subject that signs Informed Consent will be considered enrolled into the study, although they may not participate if they do not qualify for the study. In the event that a subject's or parent/guardian's ability to comprehend and communicate is compromised (per assessment of the Investigator), local regulations pertaining to Informed Consent signatures should be followed.

Some subjects may be recruited from among the investigator's own patients. In this case, the investigator will reinforce that participation is voluntary and the decision not to participate will not affect their care, now or in the future. Study staff will be available to contact if potential subjects have any further questions about the study and consent. Additionally, all subjects recruited from among the investigator's own patients will be offered the opportunity to discuss participation with a physician colleague before deciding whether or not to participate.

Subjects who have completed a previous medication trial in our program may be eligible to participate in this study, as described in the Study Design section. Other medical records on a subject will not be used at any point during this study. Participation in this study is voluntary and

subjects may withdraw from the study at any time. The IRB-approved informed consent documents will be e-signed and dated by the subject and the physician obtaining consent.

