### B. Exclusion Criteria

Subjects will be excluded from the study for **any** of the following reasons:

- Impaired intellectual capacity (clinically determined)
- Participant is unable to communicate due to delay in, or total lack of, spoken language development (grossly impaired language skills)
- Clinically unstable psychiatric conditions or judged to be at serious safety risk to self (suicidal risk) or others (within past 30 days).
- Subjects currently (within past 30 days) experiencing significant symptoms of major psychiatric disorders as clinically determined.
- Subjects with an unstable medical condition (that requires clinical attention).
- Active suicidal or homicidal ideation, as determined by clinical screening.
- The subject has a significant skin condition at the procedure sites (i.e., hemangioma, scleroderma, psoriasis, rash, open wound or tattoo).
- The subject has an implant of any kind in the head (e.g. stent, clipped aneurysm, embolised AVM, implantable shunt – Hakim valve).
- Any use of light-activated drugs (photodynamic therapy) within 14 days prior to study enrollment (in US: Visudine (verteporfin) – for age related macular degeneration; Aminolevulinic Acid- for actinic keratoses; Photofrin (porfimer sodium) – for esophageal

cancer, non-small cell lung cancer; Levulan Kerastick (aminolevulinic acid HCl) – for actinic keratosis; 5-aminolevulinic acid (ALA)- for non-melanoma skin cancer)

- Current treatment with a psychotropic medication on a dose that has not been stable for at least 4 weeks prior to initiating study treatment.
- Investigator and his/her immediate family, defined as the investigator's spouse, parent, child, grandparent, or grandchild.

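### Washout rules are inconsistent, the light-activated-drug exclusion is counted from consent rather than first irradiation, and Table I puts three secondary baselines before any washout

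*Combined protocol and SAP*

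**What the plan says.** **Who may stop a medication.** Section 7 (Washout Period) opens with patients on prohibited drugs: those "willing to discontinue the use of their medication may do so in order to be eligible for participation in this study", if the clinician judges it appropriate. It adds that, where appropriate, "medication washout will be recommended by our clinicians to participants and current providers". It then says "No subjects will be asked to discontinue ongoing exclusionary medications to participate in the study", and goes on to one case: "if the subject is already tapering the medication off for clinical reasons at the time of screening and evaluation for participation", that person becomes eligible only after the washout.

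**From which date the exclusions count.** Section 6.B excludes "Any use of light-activated drugs (photodynamic therapy) within 14 days prior to study enrollment". Section 5 defines the term: "Any subject that signs Informed Consent will be considered enrolled into the study". The other medication criterion in Section 6.B requires a psychotropic dose to have been stable for at least 4 weeks, and counts those weeks back from the start of study treatment.

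**How long it takes.** Section 3 gives a total of up to 12 weeks from enrollment, "allowing up to four weeks from the date of consent to schedule and complete the initial screening process", followed by 8 weeks of treatment. Washout is placed later still: "After the screening period, subjects who are currently taking prohibited medications as noted in exclusion criteria".

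**When the scales are taken.** Table I schedules HAM-A, HAM-D and AISRS at week 99 (screening), week 4 and week 8. Section 8 lists the same three scales as given at baseline, midpoint and endpoint. Table I has SRS-2 and the CGIs at both week 99 and week 0.

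**The concern.** Eligibility text has to give the same answer whoever reads it. Here, two clinicians could decide differently about the same patient: one who takes a prohibited drug, is not tapering it, and would be willing to stop.

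The date from which the light-activated-drug exclusion is counted is a separate problem. Followed literally, the rule examines the two weeks before consent and ignores the weeks closest to first irradiation.

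The statistical consequence comes from the design. Section 9 rests on a single-group comparison of baseline with the last assessment. It accepts that time-varying factors can bias this comparison, but expects their effect to be minimal. A medication change between the baseline rating and the first treatment is such a factor, and the protocol itself allows it. If a scale's only pre-treatment rating precedes the washout, its change score contains any effect of stopping the drug.

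**Working it through.** **1. The washout text applied to one patient.** Take a willing patient on a prohibited drug at an unchanged dose.

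- The opening sentence lets this patient stop in order to qualify.
- The next sentence has study clinicians recommend washout where appropriate.
- The later sentence says nobody will be asked to stop in order to take part.
- The only case then described is a patient already tapering for clinical reasons.

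Voluntary stopping can coexist with a promise not to ask. A recommendation from the study's own clinicians is hard to square with that promise. The text does not say whether the patient in this example may wash out.

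**2. The calendar.** Inputs: screening up to 4 weeks from consent, treatment 8 weeks and total 12 weeks (Section 3); a 14-day window ending at enrollment (Section 6.B); enrollment equal to signing consent (Section 5).

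The plan's own total reproduces: 4 + 8 = 12 weeks, or 28 + 56 = 84 days. This agreement supports reading enrollment as the date of consent.

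Set consent at day 0 and first irradiation at day g, with g up to 28 on the stated timetable.

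- The exclusion covers days -14 to 0.
- The days between consent and first irradiation that it does not cover number g, so up to about 28.
- Of the 14 days just before irradiation, the rule covers max(0, 14 - g). That is 14 days if g = 0, 7 if g = 7, and none if g is 14 or more. This shows only how much the choice of date matters; it does not propose a window.

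Washout follows screening and therefore consent. Whether a drug was used in days -14 to 0 is already settled on day 0, so stopping it later cannot cure this exclusion unless consent is taken again. The psychotropic criterion is different: it is counted back from first treatment, so what happens after consent can affect whether it is met.

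If a washout of w days follows a full screening period, the total is 28 + w + 56 = 84 + w days. That exceeds 84 for any w above zero. If screening takes only s days, 28 - s days remain.

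**3. The rating schedule.**

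| Scale | Table I, before treatment | Section 8 |
|---|---|---|
| HAM-A, HAM-D, AISRS | week 99 only | baseline, midpoint, endpoint |
| SRS-2 | weeks 99 and 0 | includes baseline |
| CGIs | weeks 99 and 0 | biweekly |

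The list of baseline-visit assessments in Section 7 omits HAM-A, HAM-D and AISRS. It also omits SRS-2, which Table I does schedule at week 0, so that list does not settle the matter.

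For a scale rated at week 99 but not at week 0, the change splits as

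Y8 - Y99 = (Y8 - Y0) + (Y0 - Y99).

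The second term contains any effect of stopping a drug between screening and week 0. Without a week 0 rating it cannot be separated. Its direction is not known.

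**4. How many participants.** The documents give no expected number of washouts. Section 4 aims to expose up to 20 subjects, so each participant who washes out would be 1/20 = 5% of that target. Two such participants, purely as an assumption, would be 10%.

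**The case against.** The strongest reply is that this is mostly loose wording. The opening of the washout text is permissive and leaves the decision with the patient and the clinician's judgment. The later sentence rules out asking, not a patient's own decision. That is fair, and it disposes of two stronger readings. A reader might infer that only patients already tapering can qualify; the text says what applies to them, not that everyone else is barred. A reader might also infer that no washout can ever make anyone eligible. That holds only for the light-activated-drug window, because the psychotropic criterion is counted from first treatment. The tension between recommending and not asking remains.

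There are also partial safeguards. Concomitant medication is recorded at weeks 99 and 0 and at later visits. Subjects who need a new medication may be discontinued if it is judged to interfere with assessing the effect, and withdrawal on investigator judgment is available. A drug used after consent could therefore be detected. But the interference rule concerns the assessment of effect, not exposure to light-activated drugs, and none of these provisions changes the exclusion.

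The four weeks are a maximum, so a quick screening would leave some room for washout. The washout language, with its references to half-life, tapering and withdrawal effects, also fits ongoing medication better than photodynamic agents. The two issues are therefore largely separate, and both need attention.

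Finally, a reader might infer that the primary SRS-2 result is contaminated by washout. The schedule does not support that. Table I takes SRS-2 (self and informant) and the CGIs at week 0, and Section 8 puts both SRS-2 forms at baseline. One sentence in the optional observer-rating text of Section 7 says measures completed at screening are repeated only at endpoint. It conflicts with that schedule, and naming week 0 as the analysis baseline would settle it. Nor is it established that every washed-out participant has a pre-washout HAM-A, HAM-D or AISRS baseline, because Section 8 and Table I disagree.

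**Conclusion.** The text is wrong as written in three limited respects.

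- The washout paragraph both recommends stopping a medication and promises that nobody will be asked to stop. It leaves the position of patients not already tapering unclear.
- The two medication exclusions are counted from different dates. For light-activated drugs, up to about 28 days between consent and first irradiation are not covered. This rests on enrollment meaning consent, which Section 5 states and the 12-week total supports. The same total leaves no time for washout after a full screening period.
- Table I conflicts with Section 8 on the baseline for HAM-A, HAM-D and AISRS. If Table I is followed, participants who wash out have pre-washout baselines on these scales.

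The bias concern reaches only those three secondary scales and only participants who wash out, whose number is unknown and may be small. No sample-size, power or type I error calculation is affected.

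**What to change.** - Reconcile Sections 3, 5, 6.B and 7 (Washout Period) so that they agree on who may stop a medication, what study clinicians may say to patients about it, and from which date each medication exclusion is counted. State where any washout falls within the study length. The clinical rule and the length of any window are for the sponsor to decide; this review proposes neither.
- Align Table I with Section 8 by taking HAM-A, HAM-D and AISRS at the existing week 0 visit, after any washout.
- State in Section 9 that week 0 values are the analysis baseline, including the SRS-2 and CGI-S ratings already scheduled there.

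The cost is protocol wording and a slightly longer week 0 visit, with no additional visit. A week 0 baseline removes the change that occurs between screening and week 0. It does not remove withdrawal effects that continue after week 0, so participants who washed out should be identified in the report.

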### **Study baseline to Endpoint (week 8)**

Participants will be prescribed to administer 2 treatments per week for 8 weeks. Virtual study visits will have a visit window of +/-3 days to facilitate scheduling. All visits will be conducted virtually via the MGH Telemedicine platform, TeleHealth, which is maintained by Partners HealthCare. In the event that TeleHealth malfunctions or a subject loses access to a device compatible with TeleHealth at scheduled time, the study visit will be completed via telephone call instead.

During the visits, the participants will be asked questions about the symptoms of ASD and general health in addition to any present side effects or changes in their medications. At weeks 2, 4 (Midpoint), and 6 the participant will be asked to fill out questionnaires.

At the baseline visit, the subject will be examined via a video call to inspect the sites of application (left and right forehead) for any possible skin lesions (e.g. laceration or signs of inflammation) which would contraindicate the treatment. The subject will then be instructed on appropriate administration of tPBM. The treatment device is classified as an “Exempt” device in accordance with the requirements of the international standard EN 62471 – Photobiological safety of lamps and lamp systems and, when used correctly, the output is less than the maximum permissible exposure (MPE) no special controls are needed for the environment it is to be used in. At the time of study implementation, the staff will be provided training on basic safety procedures relative to the use of the device. The staff will then instruct the subject on the administration of the tPBM with careful observation that the subject appropriately places the headband device. For subjects ages 9-17, the delivery of the tPBM is expected to last 10-40 minutes total (simultaneous application on the left and right forehead). The subject will be asked to rest for five minutes after the delivery of tPBM. Sites of application will be inspected at each study visit. Subjects will be instructed to administer the treatment sessions daily for eight weeks, with each session lasting 10-40 minutes. Subjects will be instructed to contact the investigator or a member of his staff at any time between visits concerning adverse events or worsening of symptoms. Subjects ages 18-59 will be instructed to administer the treatment sessions daily for eight weeks, with each session lasting 20-50 minutes. Subjects will be instructed to contact the investigator or a member of his staff at any time between visits concerning adverse events or worsening of symptoms.

The following assessments will be performed at the Baseline Visit:

- CGIs

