### Dosing

The subject will receive daily tPBM treatments for 8 weeks.

There will be 10 Niraxx treatment devices to allow up to 10 subjects simultaneously receiving treatment at any given time. The treatment will be bilateral and applied to the frontal areas with application sites on the left side and on the right side [left and right forehead centered on EEG sites on F3, Fp1 and F4, Fp2 and Fz, Fpz]. The probes delivering the LED light are embedded on the inside of a headband and are activated by a button press on a specific phone application, once accurate placement is ensured. Energy is administered with a radiation wavelength of 850 nm. Each subject will receive specific instructions on appropriate application of tPBM treatment

device at the Screening visit. All staff who deliver instructions must pass training that is approved by the MGH Laser Safety Committee.

Titration of tPBM will follow a flexible titration schedule with an option for slower titration, holding at lower dose, or lowering the dose based on tolerability and response to the tPBM as per clinician judgment. Dose will be adjusted upward per the flexible titration schedule provided the treatment is well tolerated. Titration of tPBM may occur between scheduled study visits.

Titration of tPBM will occur at different rates depending on the age of the subject at the time of treatment. Titration of tPBM may occur between scheduled study visits. For the detailed titration schedules, please refer to Table II and Table III.

The duration of irradiation for subjects ages 9-17 is 10-40 minutes at each application site (all sites are irradiated at the same time which is equivalent to 10-40 minutes of total time).

The duration of irradiation for subjects ages 9-17 is started at 10 min per day for the first week (days 1-7), increased to 20 min per day during the second week of treatment (days 7-14) and to 30 min per day at week 3 (days 14-21) of treatment. The dose will be escalated to 30 min daily as tolerated, if side-effects prevent increase (or if treatment response already occurred), a lower dose will be kept in order to ensure good tolerability and treatment adherence. At day 21, the clinician will recommend 40 min daily if no improvement in the context of good tolerability (Table II). Therefore, the duration of irradiation for subjects ages 9-17 is 10-40 minutes at each application site (all sites are irradiated at the same time which is equivalent to 10-40 minutes of total time).

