The duration of irradiation for subjects ages 18-59 is started at 20 min per day for the first week (days 1-7), increased to 30 min per day during the second week of treatment (days 7-14), to 40 min per day at week 3 (days 14-21) of treatment. The dose will be escalated to 50 min daily as tolerated, if side-effects prevent increase (or if treatment response already occurred), a lower dose will be kept in order to ensure good tolerability and treatment adherence. At day 21, the clinician will recommend 50 min daily if no improvement in the context of good tolerability (Table III). Therefore, the duration of irradiation for subjects ages 18-59 is 20-50 minutes at each application site (all sites are irradiated at the same time which is equivalent to 20-50 minutes of total time) (Lampl, Zivin et al. 2007, Schiffer, Johnston et al. 2009, Zivin, Albers et al. 2009).

Subjects diagnosed with ASD who meet all inclusion criteria, have none of the exclusion criteria, and are willing to undergo the Informed Consent process will be eligible to participate in this clinical study.

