**Table I. Study Schema**

Weeks	99	0	1	2	3	4	6	8
tPBM Device Subject Training	X	X						
tPBM Treatment (9-17)- 10 min/day		X						
tPBM Treatment (9-17)- 20 min/day			X					
tPBM Treatment (9-17)- 30 min/day				X				
tPBM Treatment (9-17)- 40 min/day					X	X	X	X
tPBM Treatment (18-59)- 20 min/day		X						
tPBM Treatment (18-59)- 30 min/day			X					
tPBM Treatment (18-59)- 40 min/day				X				
tPBM Treatment (18-59)- 50 min/day					X	X	X	X
Diagnostic Assessments								
MGH-ASD-SCL	X							
Psychiatric Evaluation & Medical History	X							
Physiological Procedures								
Physical Examination	X							X
Urine pregnancy test (females only)	X							X
Vital Signs (Height & weight)	X							X
Clinician-Rated Assessments								
MGH-SECS-C		X				X		X
CGIs	X	X		X		X	X	X
GAF	X	X		X		X	X	X
HAM-A	X					X		X
HAM-D	X					X		X
AISRS	X					X		X
CTAE		X		X		X	X	X
Concomitant Medications	X	X		X		X	X	X
Progress Note	X	X		X		X	X	X
Patient-Rated Assessments								
Demographic Interview	X							
ASRS (18+)		X				X		X
SRS-2 (Self/Informant)	X	X				X		X
BRIEF-A/P		X				X		X

Photobiomodulation in ASD

Q-LES-Q		X				X		X
TSRQ				X			X	
MGH-SECS-I (Observer)	X	X				X		X
ABCL/CBCL	X	X						X

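### The protocol sets treatment frequency both at twice weekly (16 sessions) and at daily (56 sessions) over 8 weeks, and does not say which governs

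*Combined protocol and SAP*

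**What the plan says.** Two frequencies are stated, both as current instructions.

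- **Twice weekly.** Section 7, Study baseline to Endpoint (week 8), opens with: "Participants will be prescribed to administer 2 treatments per week for 8 weeks". The sentence names no age group, phase or type of session.
- **Daily.** Section 7, Dosing, says: "The subject will receive daily tPBM treatments for 8 weeks". Under the same heading as the twice-weekly sentence, the baseline-visit text says: "Subjects will be instructed to administer the treatment sessions daily for eight weeks, with each session lasting 10-40 minutes". For adults it adds: "Subjects ages 18-59 will be instructed to administer the treatment sessions daily for eight weeks, with each session lasting 20-50 minutes".

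The dose steps are also written by the day. For children and adolescents Dosing has: "The duration of irradiation for subjects ages 9-17 is started at 10 min per day for the first week (days 1-7". For adults: "The duration of irradiation for subjects ages 18-59 is started at 20 min per day for the first week (days 1-7". Table I uses the same unit, for example "tPBM Treatment (18-59)- 50 min/day".

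Dosing allows a "flexible titration schedule with an option for slower titration, holding at lower dose, or lowering the dose". Tables II and III express the dose as maximum minutes from a given study day, and neither gives a number of sessions per week.

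**The concern.** Frequency is part of what defines this intervention, and the two statements cannot both be followed. A member of staff working from the opening of the baseline-to-endpoint text and one working from the baseline-visit instructions could give participants different regimens, each in line with the protocol. Treatment can be completed at home and the visits are virtual, so the exposure a participant receives depends heavily on those instructions.

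The study has one arm and plans to expose up to 20 participants. If the regimen is uncertain or mixed, a change in the SRS-2 or a CGI-ASD response cannot be attributed to a known exposure, and the same holds for the safety findings. Two consequences follow:

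- **Titration.** Upward steps depend on the treatment being well tolerated. The number of sessions behind that judgment differs several-fold between the two readings.
- **Adherence.** Section 1 reports 98% adherence at the adult stage without stating a denominator. A rate based on prescribed sessions would mean different things under the two frequencies.

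**Working it through.** The documents print no session total, so there is no stated figure to reproduce. The counts follow from the stated frequencies and the 8-week duration.

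**Inputs**
- Duration: 8 weeks (Sections 2, 3 and 7).
- Frequency A: 2 per week (Section 7, Study baseline to Endpoint).
- Frequency B: daily, read as one session on each of 7 days (Section 7, Dosing and baseline-visit instructions).
- Maximum minutes by week: 10, 20, 30, then 40 for five weeks (ages 9-17); 20, 30, 40, then 50 for five weeks (ages 18-59) (Tables I to III).

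**Sessions per participant** (sessions per week × weeks)
- A: 2 × 8 = 16
- B: 7 × 8 = 56
- Ratio: 56 / 16 = 3.5

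For 20 exposed participants, the upper limit in Section 4, this is 20 × 16 = 320 against 20 × 56 = 1,120 sessions.

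**Maximum minutes per participant, stepping by whole weeks**

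| Ages | Sum of weekly values | A (× 2) | B (× 7) |
|---|---|---|---|
| 9-17 | 10 + 20 + 30 + 5 × 40 = 260 | 520 | 1,820 |
| 18-59 | 20 + 30 + 40 + 5 × 50 = 340 | 680 | 2,380 |

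**Sensitivity to the step day.** If the steps fall exactly on days 7, 14 and 21, the first three steps last 6, 7 and 7 days and the last lasts 36.
- Ages 9-17, daily: 6 × 10 + 7 × 20 + 7 × 30 + 36 × 40 = 1,850. Twice weekly: 520 to 550, depending on whether sessions fall on step days. Ratio 1,850/550 = 3.36 to 1,850/520 = 3.56.
- Ages 18-59, daily: 6 × 20 + 7 × 30 + 7 × 40 + 36 × 50 = 2,410. Twice weekly: 680 to 710. Ratio 2,410/710 = 3.39 to 2,410/680 = 3.54.

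**Sessions completed before each step, for steps on days 7, 14 and 21**
- Daily: 7 − 1 = 6, 14 − 1 = 13, 21 − 1 = 20.
- Twice weekly: 1-2, 3-4, 5-6; the lower value applies if a session falls on the step day.

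The Dosing text places days 7 and 14 in two adjoining steps. If each step instead begins the day after, the counts are 7, 14 and 21 against 2, 4 and 6.

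**Adherence, if defined as completed over prescribed sessions (an assumption).** Sixteen completed sessions are 16/16 = 100% under A and 16/56 = 28.6% under B.

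**Readings that might reconcile the two**
- *A subgroup or phase:* the twice-weekly sentence has no such limit, and the daily instructions cover both age groups.
- *Flexible titration:* the rule concerns speed of titration and dose level, and its tables express dose in minutes.
- *The tPBM Self-Report Questionnaire:* Section 8 offers it at weeks 3 and 6, once at least two sessions have been given. Either frequency meets that condition.
- *Order of precedence:* none is stated.

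**The case against.** The strongest reply is that the conflict is lopsided. Twice weekly appears in a single sentence, while daily use or minutes per day appears in Dosing, in the instructions for both age groups and in Table I. The single sentence may be leftover text, and staff working from the participant instructions would meet the daily wording. That may lower the practical risk. It does not remove the contradiction: the documents nowhere call the sentence obsolete, it opens the section that governs conduct from baseline to endpoint, and it is worded as a prescription. A count of mentions is not a rule of precedence.

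Several narrower objections stand in part:

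- The twice-weekly minute totals combine that frequency with steps written per day, a combination no section specifies. They are also maxima under flexible titration. The conclusion therefore rests on sessions, not minutes.
- Adherence is neither a listed outcome in Section 7 nor an analysis in Section 9, and the 98% may count something other than sessions. The 100% against 28.6% contrast is illustrative only.
- The totals for 20 participants are upper limits and include adults already treated in this ongoing study, whose instructions can no longer be changed.

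**Conclusion.** The contradiction is real and nothing in the documents resolves it. The planned number of sessions is either 16 or 56 per participant, a ratio of 3.5. This assumes that daily means once a day on seven days a week and that the treatment period is eight full weeks. Moving the step days shifts the ratio of minutes only to between about 3.4 and 3.6.

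The Wilcoxon signed rank and McNemar tests are valid or not regardless of this point. What is missing is a single definition of the treatment to which their results apply. That needs correcting before the study proceeds, because two incompatible treatment instructions cannot both stand. The documents do not show which frequency is intended, and this review takes no position on it.

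**What to change.** The sponsor should decide the intended frequency and reconcile to it, in one amendment, the Dosing text, the opening of Study baseline to Endpoint (week 8), the baseline-visit instructions for both age groups and Table I. This should be done before further participants are instructed. Stating the frequency beside the minutes in Tables II and III would help keep the two from drifting apart again. If adherence is to be reported, its denominator should be defined from the same number.

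Since the study is ongoing, the report should also state which frequency participants already treated were told to follow.

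The cost is amendment wording and matching participant instructions. No participants are added and the statistical analysis does not change.
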